**APPENDIX 7: NEW YORK HEART ASSOCIATION CLASSIFICATION****Table 15: New York Heart Association Classification**

Class I	Subjects with no limitation of activities; they suffer no symptoms from ordinary activities.
Class II	Subjects with slight, mild limitation of activity; they are comfortable with rest or with mild exertion.
Class III	Subjects with marked limitation of activity; they are comfortable only at rest.
Class IV	Subjects who should be at complete rest, confined to bed or chair; any physical activity brings on discomfort and symptoms occur at rest.

Approved

**APPENDIX 8: ALGORITHMS FOR EARLY DETECTION AND TREATMENT OF IMMUNE RELATED ADVERSE EVENTS (IRAES)**

The guidelines provided below have been adapted from the European Society for Medical Oncology (ESMO) clinical practice guidelines for management of toxicities from immunotherapy (Haanen 2018). Please refer to the full publication for management of irAEs not specifically discussed below (Appendix 9). These may be supplemented by discussions with the sponsor's medical monitor as well as institutional guidelines on management of these toxicities.

Diarrhea and Colitis			
Grade	FPT155 Dosing	Management Escalation Pathway	Assessment and Investigations
Grade 1 Diarrhea : <4 stools/ day over baseline Colitis : asymptomatic	No delay or missed dose	Symptomatic management: Oral fluids, loperamide, avoid high fiber/lactose diet Persists >14 days or worsens, treat as Grade 2	Close monitoring for worsening symptoms Patient education to immediately report worsening symptoms
Grade 2 Diarrhea : 4-6 stools per day over baseline; Outpatient management if appropriate Colitis : abdominal pain, blood in stool	Delay or miss dose Reinitiate upon recovery to $\leq$ Grade 1	Symptomatic management: Oral fluids, loperamide, avoid high fiber/lactose diet Persists > 3 days or worsens 0.5-1.0 mg/kg (methyl)prednisolone or oral equivalent Persists >3 days or worsens, treat as Grade 3/4	Clinical safety labs (eg, CBC, chemistry, CRP) Stool microscopy for leukocytes/ova/parasites, culture, viral polymerase chain reaction (PCR), clostridium difficile toxin, cryptosporidia
Grade 3/4 Diarrhea (G3) : $\geq$ 7 stools per day over baseline; incontinence; requires hospitalization Colitis (G3) : severe abdominal pain, fever, ileus, peritoneal signs; medical intervention indicated G4 : Life-threatening, perforation	Permanently discontinue FPT155	1.0-2.0 mg/kg (methyl) prednisolone IV or IV equivalent Persists > 3 days, infliximab 5 mg/kg (if no contraindication)	Assess as above Urgent gastrointestinal (GI) consult and abdominal CT and/or sigmoid/colonoscopy

Hepatitis			
Grade	FPT155 Dosing	Management Escalation Pathway	Assessment and Investigations
Grade 1 AST or ALT > ULN-3.0 x ULN and/or T. bili > ULN-1.5 x ULN	No delay or missed dose	N/A	Close monitoring for worsening symptoms or laboratory parameters
Grade 2 AST or ALT > 3.0 -≤ 5 x ULN and/or T. bili > 1.5- ≤ 3 x ULN	Delay or miss dose Reinitiate upon recovery to ≤Grade 1	Monitor liver function tests (LFTs) every 3 days	Review concomitant medications (e.g. statins, antibiotics) alcohol use Perform liver screen: Hepatitis A/B/C serology, Hepatitis E PCR, anti- smooth muscle antibody (SMA)/anti-nuclear antibody (ANA)/liver kidney microsome (LKM)/soluble liver antigen (SLA) /lipoprotein (LP)/ Anti-liver cytosol 1 autoantibody (LCI), iron studies Consider Liver imaging
Grade 3/4 AST or ALT >5 x ULN or T.bili >3 x ULN	Permanently discontinue FPT155	Monitor LFTs every 1-2 days 1.0-2.0 mg/kg (methyl) prednisolone IV or IV equivalent (2 mg/kg/day IV methylprednisolone for Grade 4 AEs)	Assess as above Refer to Hepatologist Liver imaging Consider liver biopsy for Grade 4 AEs

Renal Adverse Events			
Grade	FPT155 Dosing	Management Escalation Pathway	Assessment and Investigations
Grade 1 Creatinine $>1.5 \times$ baseline or $> \text{ULN} \times 1.5 \times \text{ULN}$	No delay or missed dose	Monitor serum creatinine weekly	Review hydration status, medications, urinalysis/culture if urinary tract infection symptoms Dipstick urine and send for protein assessment. If obstruction suspected: renal ultrasound +/- doppler to exclude obstruction/clot If worsens treat as below
Grade 2-3 G2 : creatinine $> 1.5-3 \times$ baseline or $> 1.5-3 \times \text{ULN}$ G3 : creatinine $> 3 \times$ baseline or $> 3-6 \times \text{ULN}$	Delay or miss dose Reinitiate upon recovery to $\leq \text{Grade 1}$	Monitor serum creatinine every 2-3 days 0.5-1.0 mg/kg/day methylprednisolone IV or oral equivalent Persists $>7$ days or worsens, treat as Grade 4	Assess as above If proteinuria: perform 24 h urine collection or urine protein to creatinine ratio (UPCR) Refer to nephrologist
Grade 4 Creatinine $> 6 \times \text{ULN}$	Permanently discontinue FPT155	Monitor serum creatinine daily 1.0-2.0 mg/kg methyl prednisolone IV or IV equivalent	Assess as above Refer to nephrologist Consider renal biopsy

Pneumonitis			
Grade	FPT155 Dosing	Management Escalation Pathway	Assessment and Investigations
Grade 1 Radiographic changes only Ground glass change, non-specific interstitial pneumonia	Consider delay or miss dose	Monitor symptoms every 2-3 days Re-image $\leq$ every 3 weeks	Consider pulmonary and Infectious disease referral Clinical safety labs (eg, CBC, chemistry, CRP) Consider sputum sample and screening for viral opportunistic or specific bacterial infections
Grade 2 Mild/moderate new symptoms Dyspnea, cough, chest pain	Delay or miss dose Reinitiate upon recovery to $\leq$ Grade 1	Monitor symptoms daily Re-image $\leq$ weekly 1.0 mg/kg/day methylprednisolone IV or oral equivalent Consider pneumocystis prophylaxis	Assess as above Pulmonary and Infectious disease referral Consider bronchoscopy, lung biopsy
Grade 3/4 Severe new symptoms New/worsening hypoxia Life threatening Difficulty in breathing, Acute Respiratory Distress Syndrome (ARDS)	Permanently discontinue FPT155	2.0-4.0 mg/kg/day methylprednisolone IV or IV equivalent Persists $>2$ days, add infliximab 5 mg/kg (if no contraindication) or additional immunosuppression (e.g., mycophenolate mofetil [MMF], cyclophosphamide, intravenous immunoglobulin G [IVIG])	Hospitalize and assess as above Pulmonary and Infectious disease referral Consider bronchoscopy, lung biopsy

Skin Adverse Events			
CTCAE Grade	FPT155 Dosing	Management Escalation Pathway	Assessment and Investigations
Grade 1/2 G1 : Skin rash with or without symptoms; <10% body surface area (BSA) G2 : rash covers 10-30% BSA	No delay or missed dose	Avoid skin irritants and sun exposure Symptomatic therapy (e.g. antihistamines, topical steroids and emollients) Persists >1-2 weeks, consider 0.5-1.0 mg/kg/ day methylprednisolone IV or oral equivalent	Physical exam, exclude other causes (eg viral infections, concomitant medication)
Grade 3/4 G3 : rash covers >30% BSA or G2 with substantial symptoms G4 : skin sloughing >30% BSA with associated symptoms or life-threatening consequences	Delay or miss dose or discontinue FPT155 permanently Reinitiate upon recovery to $\leq$ Grade 1	Symptomatic therapy (e.g. antihistamines, topical steroids and emollients) 1.0-2.0 mg/kg/day methylprednisolone IV or IV equivalent	Refer to dermatologist Consider skin biopsy

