### 6.9.3 Dose Modification and Delay Criteria

Dose reductions or delays for FPT155 may be permitted for patients on treatment beyond the DLT evaluation interval in Phase 1a dose escalation, any patients in the Phase 1a dose exploration, or any patients in Phase 1b per the guidelines in [Table 9](#). Dose reductions can be assessed using local laboratories. If a patient in Phase 1a dose escalation requires a dose reduction of FPT155 during the DLT period, they will be considered a DLT and be permanently discontinued from FPT155.

Dose reductions and delays for FPT155-related AEs or laboratory abnormalities should follow the guidelines outlined in [Table 9](#). Refer to Section [6.9.4](#) and [Appendix 10](#) for additional specific guidelines for irAEs and CRS. Any variations from these guidelines must be discussed with the Sponsor prior to dosing and must take into consideration the overall benefit and risks for the patient of continued participation in the study.

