**Table 9: Dose Modification and Delay Criteria for FPT155 (Non-Infusion Toxicity)**

FPT155-related Toxicity Grade	Dose Schedule	New FPT155 Dose
Grade 1	No delay or missed dose required	100% of dose
Grade 2	Delay or miss dose until recovery to Grade 1 for suspected irAEsa and CRSb No delay or missed dose required for other AEs	100% of dose
Grade 3 (first occurrence)	Delay or miss dose until recovery to baseline or Grade 1	If recovery to baseline or Grade 1 within 14 days, may resume at 100% of starting dose or 1 dose lower c
Grade 3 (second occurrence)	Delay or miss dose until recovery to baseline or Grade 1	If recovery to baseline or Grade 1 within 14 days, may resume at 1 level lower b than previous dose or discontinue
Grade 3 (third occurrence) Grade 3 which does not recover to baseline or Grade 1 within 14 days Any Grade 4	Permanently Discontinue	N/A

a Refer to Section 6.9.4 and [Appendix 8](#) for additional guidance regarding irAEs

b Refer to Section 6.9.5 and [Appendix 10](#) for additional guidance regarding CRS

c E.g., 1 dose level lower for patients treated at 70.0 mg is 42.0 mg; 1 dose level lower for patients treated at 42.0 mg is 21.0 mg.

Abbreviations: AE = adverse event; irAEs = immune-related adverse events; CRS = cytokine release syndrome.

The first dose of each cycle is considered Day 1 of each cycle. Cycles will repeat every 21 days unless there is a treatment delay. A treatment delay of longer than 4 weeks should be discussed with the medical monitor prior to continuation of that subject on study. Treatment is administered Q3W until disease progression, unacceptable toxicity, or until the patient meets any of the other protocol-specified withdrawal criteria.

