#### 6.9.4 Management of irAEs

Based on the underlying mechanism action, irAEs associated with the anti-CTLA-4 class of drugs (eg, ipilimumab) may potentially be observed with FPT155. Given the differentiated mechanism of action of FPT155 and the absence of any clinical data, the actual timing, incidence and severity of these AEs may differ significantly from anti-CTLA-4 therapies. General guidelines for management of suspected irAEs are provided here. These may be supplemented by discussions with the Sponsor as well as institutional guidelines on management of these toxicities.

In all instances, patients should be thoroughly evaluated to rule out a non-inflammatory etiology (eg, disease progression, concomitant medication, infections etc.). Symptomatic or topical therapy should be considered for most Grade 1 or 2 events unless otherwise specified in [Appendix 8](#). Corticosteroids are the primary therapy for irAEs. Corticosteroids should be tapered over at least 2-4 weeks in patients experiencing Grade 2 AEs and at least 4-8 weeks in

patients experiencing Grade 3/4 AEs. Appropriate antiviral, antifungal (e.g. pneumocystis) and antibacterial prophylaxis must be considered in patients receiving corticosteroids for prolonged durations to reduce the risk of opportunistic infections. More potent immunosuppressive agents such as TNF inhibitors (eg, infliximab) should be considered for events not responding to systemic steroids. Refer to [Appendix 8](#) for additional specific guidelines for individual irAEs.

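### The Appendix 8 skin table leaves restart of FPT155 open after a Grade 4 skin event that Table 9 stops permanently; its Grade 2 rash rule also needs reconciling with Table 9

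*Protocol*

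**What the plan says.** Section 6.9.3 directs sites to Table 9 for delays and reductions due to FPT155-related toxicity. Table 9 has three relevant entries:

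- Grade 2: "Delay or miss dose until recovery to Grade 1 for suspected irAEsa and CRSb" (the stray final letters are footnote marks). Other Grade 2 events need no hold. Footnote a refers the reader to Section 6.9.4 and Appendix 8.
- Grade 3, first occurrence: "If recovery to baseline or Grade 1 within 14 days, may resume at 100% of starting dose or 1 dose lower". A second occurrence allows resumption one level lower, or discontinuation.
- Permanent discontinuation: a third Grade 3 occurrence, plus "Grade 3 which does not recover to baseline or Grade 1 within 14 days Any Grade 4".

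Section 6.9.3 also refers to Section 6.9.4 for immune-related events, and Section 6.9.4 sends sites to Appendix 8 "for additional specific guidelines for individual irAEs".

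The Appendix 8 skin table has two merged rows. The Grade 1/2 row, where Grade 2 is "rash covers 10-30% BSA", continues dosing. The Grade 3/4 row carries the dosing instruction "Delay or miss dose or discontinue FPT155 permanently Reinitiate upon recovery to" Grade 1 or lower. That row covers Grade 3 rash, Grade 2 rash with substantial symptoms, and Grade 4 (sloughing over more than 30% of body surface with associated symptoms, or life-threatening consequences).

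**The concern.** A merged cell applies every option in it to every grade in the row. Read on its own, the Grade 3/4 skin cell lets a site hold FPT155 after a life-threatening skin reaction and give it again on recovery. The main rule rules that out. Appendix 8 is the page a site is likely to open when managing a rash, so the permissive wording sits where it is most likely to be used.

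The Grade 2 difference matters less. Its consequence is inconsistent practice: treatment interruptions due to adverse events form part of a Phase 1b primary endpoint (Section 3.0), so some rash-related delays would reflect which page the site followed. Analyses are descriptive (Section 9.0), so the effect stops at those counts.

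**Working it through.** There is no sample size, power or error rate to reproduce. The check is a grade-by-grade comparison of the two tables for a skin event related to FPT155.

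| Grade | Table 9 | Appendix 8 skin table | Result |
|---|---|---|---|
| 1 | Continue | Continue | Agree |
| 2, suspected immune-related, no substantial symptoms | Hold until Grade 1 | Continue | Differ |
| 2, suspected immune-related, substantial symptoms | Hold until Grade 1 | Treated with Grade 3: hold or stop | Compatible |
| 2, not suspected immune-related or CRS | Continue | Continue | Agree |
| 3 | Hold; restart if recovered within 14 days; stop at third occurrence | Hold or stop; restart at Grade 1 or lower | Compatible; skin table silent on the limits |
| 4 | Stop permanently | Hold or stop; restart at Grade 1 or lower | Skin table permits what Table 9 forbids |

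**The other Appendix 8 tables.** Five are arranged by grade: colitis, hepatitis, renal, pneumonitis and skin. Hypophysitis is arranged by symptoms and is not counted. At Grade 4, four of the five read "Permanently discontinue FPT155" with no restart option; skin is the exception. At Grade 2, the same four hold the dose and skin does not.

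**The attached guideline (Appendix 9).**

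- At Grade 4, its summary table calls for permanent discontinuation, and its skin diagnosis section says the same for life-threatening cases. Its narrative on managing rash speaks only of interrupting treatment at Grade 4, so the source is not uniform.
- At Grade 2, the narrative allows continuation with weekly checks, then interruption until Grade 1 if the rash has not resolved. The skin table omits that interruption step, although it does suggest considering systemic steroids when a rash persists beyond one to two weeks.

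**Is there a rule on which table prevails?** Neither Section 6.9.3 nor Section 6.9.4 states one. Footnote a is attached to the Grade 2 immune-related entry. The Grade 4 entry has no footnote.

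**The case against.** The strongest reply is that the two texts can be read together. At Grade 4 a site that stops permanently satisfies both. To re-dose, it would have to overlook Table 9 and also the sentence "Any variations from these guidelines must be discussed with the Sponsor prior to dosing". A delay beyond four weeks needs discussion with the medical monitor as well. This stands as far as it goes: the skin cell offers an option and does not command a restart. It does not remove the option. The sentence on variations follows references to both Table 9 and Section 6.9.4, so a site following Appendix 8 may not think it is varying from anything.

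At Grade 2 the reply is stronger. Footnote a sits on the very entry in question, so a general hold refined by organ-specific guidance is a natural reading, and Appendix 9 supports continuing. What remains is that the text calls Appendix 8 additional guidance and never says that it overrides the hold.

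It is also fair to say that open wording is not unique to skin. The severe hypophysitis row likewise allows either a delay or a permanent stop. Appendix 8 also departs from Table 9 at Grade 3 for colitis, hepatitis and pneumonitis, where it stops permanently. Departure alone is therefore not an error. Those Grade 3 departures are stricter than Table 9, whereas the Grade 4 skin option is looser.

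**Conclusion.** The Grade 4 skin wording is wrong as written and should be corrected on safety grounds. This rests on the text alone: Table 9's Grade 4 stop is unqualified, and nothing in Sections 6.9.3 or 6.9.4 withdraws the restart option from the skin cell. The Grade 2 difference is a secondary clarification, confined to rash judged a suspected immune-related event and without substantial symptoms.

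A reader might infer more than this, and the documents do not support it:

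- That Appendix 8 directs restart after Grade 4. Permanent discontinuation is one of the choices in the cell.
- That dosing through Grade 2 rash is unsafe. Appendix 9 allows it, with weekly checks.
- That Grade 3 is also in conflict. The skin row only leaves out Table 9's time and recurrence limits.
- That a known share of patients would meet opposite Grade 2 instructions. Appendix 9 reports rash in about 24% on ipilimumab, with Grade 3 or 4 below 3%, which leaves roughly 21% at Grade 1 or 2 (24 − 3). Turning that into a count needs the Grade 2 share, the share judged suspected immune-related, the share without substantial symptoms, and ipilimumab as a stand-in for FPT155. The documents supply none of these, and a rash that settles before the next dose triggers no hold under either rule. No prevalence figure is claimed.

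**What to change.** 1. Split the Grade 3/4 skin row. Grade 4: permanent discontinuation of FPT155. Grade 3, including Grade 2 with substantial symptoms: delay and reinitiate at Grade 1 or lower, subject to Table 9's 14-day and repeat-occurrence limits.
2. Add an exception to Table 9's Grade 2 immune-related hold: rash without substantial symptoms may continue with weekly checks and is interrupted until Grade 1 if unresolved. Repeat it in the skin table.
3. Do not add a general sentence that the stricter source applies. It would reach the endocrinopathy rules, for example turning continued dosing into a hold for a vague-symptom hypophysitis graded 2. If a precedence sentence is wanted, limit it to the colitis, hepatitis, renal, pneumonitis and skin tables. That keeps the Appendix 8 permanent stops for Grade 3 colitis, hepatitis and pneumonitis, which Table 9 alone would allow to resume.

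The cost is a small protocol amendment with IRB/IEC approval (Section 10.1.3), which can go into the next one. It needs no new data collection and no SAP change.

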## Endocrinopathy

Patients with unexplained symptoms such as fatigue, myalgias, mental status changes, or constipation should be investigated for the presence of thyroid, pituitary or adrenal endocrinopathies. An endocrinologist should be consulted if an endocrinopathy is suspected. Thyroid-stimulating hormone (TSH) and free thyroxine (free T4) levels should be obtained to determine if thyroid abnormalities are present. If a subject has thyroid dysfunction and concomitant symptoms (ie, fatigue), the subject should be monitored more frequently and be treated as per standard medical practice. Appropriate hormone replacement therapy should be instituted if an endocrinopathy is documented.

Specific guidance for management of suspected hypophysitis is provided below.

Symptoms	FPT155 Dosing	Management Escalation Pathway	Assessment and Investigations
Vague symptoms (eg, mild fatigue, anorexia), no headache or Asymptomatic	No delay or missed dose	Perform pituitary axis assessment* to confirm diagnosis	Initiate hormone replacement therapy as necessary after consultation with endocrinologist
Moderate symptoms, ie, headache but no visual disturbance or Fatigue/mood alteration but haemodynamically stable, no electrolyte disturbance	Delay or miss dose Reinitiate upon recovery to baseline	Perform pituitary axis assessment* to confirm diagnosis Oral prednisolone 0.5-1 mg/kg/day (Taper over at least 1 month) If no improvement in 48h, treat as severe (see below)	MRI (pituitary protocol), exclude brain metastases Consider formal visual field assessment Refer to endocrinologist
Severe mass effects (ie, severe headache, any visual disturbance) or severe hypoadrenalinism (ie, hypotension, severe electrolyte imbalance)	Delay or miss dose or permanently discontinue FPT155	Perform pituitary axis assessment* to confirm diagnosis Initiate IV methylprednisolone 1 mg/kg (Taper over at least 1 month) Analgesia as needed for headache (discuss with neurologist if resistant to paracetamol and nonsteroidal anti-inflammatory drugs [NSAIDs])	MRI (pituitary protocol), exclude brain metastases Consider formal visual field assessment Refer to endocrinologist

\*Pituitary Axis assessment: 9 am serum cortisol (or random if unwell and treatment cannot be delayed), adrenocorticotropic hormone (ACTH), TSH/free T4, luteinizing hormone (LH), follicle-stimulating hormone (FSH), oestradiol if premenopausal, testosterone in men, insulin-like growth factor-1 (IGF-1), prolactin

**APPENDIX 9: MANAGEMENT OF TOXICITIES FROM IMMUNOTHERAPY:  
ESMO CLINICAL PRACTICE GUIDELINES FOR DIAGNOSIS,  
TREATMENT AND FOLLOW-UP**

Approved

## CLINICAL PRACTICE GUIDELINES

# Management of toxicities from immunotherapy: ESMO Clinical Practice Guidelines for diagnosis, treatment and follow-up†

J. B. A. G. Haanen, F. Carbonnel, C. Robert, K. M. Kerr, S. Peters, J. Larkin & K. Jordan, on behalf of  
the ESMO Guidelines Committee\*

Netherlands Cancer Institute, Division of Medical Oncology, Amsterdam, The Netherlands; Department of Gastroenterology, Kremlin Bicêtre Hospital, Assistance Publique-Hôpitaux de Paris (AP-HP), Paris, France; Department of Medicine, Dermatology Unit, Gustave Roussy Cancer Campus, Villejuif, France; Department of Pathology, Aberdeen University Medical School & Aberdeen Royal Infirmary, Aberdeen, UK; Oncology Department, Centre Hospitalier Universitaire Vaudois (CHUV), Lausanne, Switzerland; Royal Marsden Hospital NHS Foundation Trust, London, UK; Department of Medicine V, Hematology, Oncology and Rheumatology, University Hospital of Heidelberg, Heidelberg, Germany

\*Correspondence to: ESMO Guidelines Committee, ESMO Head Office, [name]. E-mail: [contact]

†Approved by the ESMO Guidelines Committee: May 2017.

### General aspects of immune checkpoints blockade

#### Incidence and epidemiology

Immunotherapy with monoclonal antibodies (MoAbs) targeting cytotoxic T lymphocyte-associated antigen 4 (CTLA4) and the programmed death-1 receptor (PD-1) and its ligand PD-L1 has become standard of care for an increasing number of indications (Table 1). Therefore, an increasing number of patients will be exposed to these drugs with a chance of developing toxicities from these treatments. Depending on the immune checkpoint that is targeted, the incidence of toxicity varies. Toxicities from immune checkpoint inhibitors (ICPis) can be divided into infusion reactions and immune-related adverse events (irAEs) or adverse events of special interest (AEoSI). The latter will be the subject of these Clinical Practice Guidelines. Any organ or tissue can be involved, although some irAEs occur much more commonly than others. The most frequently occurring irAEs affect skin, colon, endocrine organs, liver and lungs. Others are very infrequent, but may be very serious, even lethal, such as neurological disorders and myocarditis.

